5.5. Investigational Product Storage

The investigator, or an approved representative, eg, pharmacist, will ensure that all investigational products, including marketed products, are stored in a secured area with

controlled access under required storage conditions and in accordance with applicable regulatory requirements.

Investigational products should be stored in their original containers and in accordance with the labels. PF-06873600 should be stored as described on the label and as outlined in the IP manual and patient dosing diaries.

Any storage conditions stated in the SRSD will be superseded by the storage conditions stated on the product label (for each combination drug letrozole/fulvestrant).

Site systems must be capable of measuring and documenting (for example, via a log), at a minimum, daily minimum and maximum temperatures for all site storage locations (as applicable, including frozen, refrigerated, and/or room-temperature products). This should be captured from the time of investigational product receipt throughout the study. Even for continuous-monitoring systems, a log or site procedure that ensures active evaluation for excursions should be available. The intent is to ensure that the minimum and maximum temperature is checked each business day to confirm that no excursion occurred since the last evaluation and to provide the site with the capability to store or view the minimum/maximum temperature for all nonworking days upon return to normal operations. The operation of the temperature monitoring device and storage unit (for example, refrigerator), as applicable, should be regularly inspected to ensure they are maintained in working order.

Any excursions from the product label storage conditions should be reported to Pfizer upon discovery. The site should actively pursue options for returning the product to the storage conditions described in the labeling, as soon as possible. Deviations from the storage requirements, including any actions taken, must be documented and reported to Pfizer.

Once an excursion is identified, the investigational product must be quarantined and not used until Pfizer provides permission to use the investigational product. It will not be considered a protocol deviation if Pfizer approves the use of the investigational product after the temperature excursion. Use of the investigational product prior to Pfizer approval will be considered a protocol deviation.

Specific details regarding information the site should report for each excursion will be provided to the site.

Receipt of materials, door opening and closing, and other routine handling operations where the products are briefly out of the temperature range described in the labeling are not considered excursions.

Site staff will instruct patients on the proper storage requirements for take home investigational products.

5.6. Investigational Product Accountability

The investigator site must maintain adequate records documenting the receipt, use, loss, or other disposition of the investigational product supplies. All investigational products will be accounted for using a drug accountability form/record.

All bottles of study drug, including any unused tablets, must be returned to the investigator by the patient at designated study visits and at the end of the trial.

5.6.1. Destruction of Investigational Product Supplies

The sponsor or designee will provide guidance on the destruction of unused investigational product (eg, at the site). If destruction is authorized to take place at the investigator site, the investigator must ensure that the materials are destroyed in compliance with applicable environmental regulations, institutional policy, and any special instructions provided by Pfizer, and all destruction must be adequately documented.

For all bottles returned to the investigator by the patient, the investigator will maintain the returned supply until destruction is authorized. Pfizer will provide instructions as to the disposition of any unused investigational product.

5.7. Concomitant Treatment(s)

Concomitant treatment considered necessary for the patient's well-being may be given at discretion of the treating physician.

All concomitant treatments, blood products, as well as nondrug interventions (eg, paracentesis) received by patients from screening until the end of study visit will be recorded on the CRF.

Because inhibition of CYP3A4/5 isoenzymes may increase PF-06873600 exposure leading to potential increases in toxicities, the use of known strong CYP3A4/5 inhibitors is not permitted within 5 half-lives of the respective CYP3A4/5 inhibitor(s), prior to the first dose of PF-06873600.

Strong CYP3A4/5 inhibitors may include grapefruit juice or grapefruit/grapefruit related citrus fruits (eg, Seville oranges, pomelos), ketoconazole, miconazole, itraconazole, voriconazole, posaconazole, clarithromycin, telithromycin, indinavir, saquinavir, ritonavir, nelfinavir, amprenavir, fosamprenavir, nefazodone, lopinavir, troleandomycin, mibefradil, and conivaptan.

Use of moderate CYP3A4/5 inhibitors should be avoided if possible, and any use needs to be reviewed and approved by the sponsor. Moderate CYP3A4 inhibitors may include erythromycin, verapamil, atazanavir, fluconazole, darunavir, diltiazem, delavirdine, aprepitant, imatinib, tofisolam, ciprofloxacin, and cimetidine.

Because induction of CYP3A4/5 isoenzymes may decrease PF-06873600 exposure leading to potential decrease in efficacy, the use strong CYP3A4/5 inducers is not permitted within

5 half-lives of the respective CYP3A4/5 inducer(s), prior to the first dose of PF-06873600. Strong CYP3A4/5 inducers may include phenobarbital, rifampin, phenytoin, carbamazepine, rifabutin, rifapentin, clevidipine, and St. John's Wort. In addition, the use of moderate CYP3A4/5 inducers warrants caution. Moderate CYP3A4/5 inducers may include bosentan, efavirenz, etravirine, modafinil, and nafcillin (www.druginteractioninfo.org).²⁶

Concomitant use of PF-06873600 and a CYP3A4/5 substrate may increase the exposure of the CYP3A4/5 substrate. Therefore, caution is warranted for the coadministration of PF-06873600 with CYP3A4/5 substrates with a narrow therapeutic indices. CYP3A4/5 substrates of a narrow therapeutic indices, may include astemizole, terfenadine, cisapride, pimozide, quinidine, tacrolimus, cyclosporine, sirolimus, (alfentanil and fentanyl, excluding transdermal patch), or ergot alkaloids (ergotamine, dihydroergotamine) (www.druginteractioninfo.org).²⁶

Concomitant use of PF-06873600 and a substrate of the MATE1 or MATE2K renal transporters may increase the exposure of the MATE1 or MATE2K substrate. Therefore, caution is warranted for the coadministration of PF-06873600 with MATE1 or MATE2K substrates. MATE1 or MATE2K substrates may include metformin, cimetidine, procainamide, cephalexin, acyclovir, gancyclovir, fexofenadine (www.druginteractioninfo.org).²⁶

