1.3.2. Nonclinical Pharmacokinetics (PK)

Following intravenous (IV) administration, the non-clinical PK of PF-06873600 was characterized by low plasma clearance (CL_p) in rat, dog and monkey (8 to 13 mL/min/kg) and high in mouse (63 mL/min/kg). PF-06873600 exhibits a volume of distribution at steady state (V_{ss}) of between 0.6 to 1.3 L/kg across species. PF-06873600 exhibits moderate to rapid absorption (time to maximum concentration (T_{max}) = 0.5 to 4 hours) after oral administration in preclinical species. The oral bioavailability of PF-06873600 was moderate and observed to range between 29% to 59% in the relevant preclinical species. Following repeat oral dosing in mice and dogs, systemic exposure increased with an increase in dose with no evidence of sex-related differences in exposure in either species. There was no accumulation of exposure after multiple doses on Day last when compared to the exposure on Day 1 in either species.

In vitro studies suggest PF-06873600 is a substrate for the efflux transporters human P-glycoprotein (P-gp) and human breast cancer resistance protein (BCRP). As a result of the high passive permeability exhibited by PF-06873600 and moderate % F observed in relevant preclinical species (rat, dog, and monkey), the oral absorption of PF-06873600 in humans is predicted to be moderate.

Renal and/or biliary excretion of PF-06873600 in rats and dogs was minimal. In vitro studies using Sandwich Cultured Human Hepatocytes (SCHH) demonstrate that PF-06873600 does not exhibit biliary excretion and therefore biliary excretion is predicted to be minimal in humans.

Following in vitro evaluation, the primary mechanisms of clearance for PF-06873600 in preclinical species and humans appears to be oxidation mediated primarily by cytochrome P450 (CYP) enzymes, predominantly CYP3A4. No unique human metabolites were identified. Mean IC₅₀ values for inhibition of CYPs 1A2, 2B6, 2C8, 2C9, 2D6, and 3A4/5 were >100 µM, while the IC₅₀ value for CYP2C19 was 92.8 µM. PF-06873600 demonstrated time-dependent inhibition (TDI) of CYP3A4 enzymes but did not exhibit induction of CYP1A2, CYP3A4, or CYP2B6. PF-06873600 is not likely to demonstrate drug-drug interaction (DDI) with MDR1, OATP1B1, OATP1B3, OAT1, OAT3, OCT1, or OCT2; however, PF-06873600 may exhibit DDI mediated by inhibition of BCRP, MATE1, or MATE2K.

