16. Investigator site staff members directly involved in the conduct of the study and their family members, site staff members otherwise supervised by the investigator, or patients who are Pfizer employees, including their family members, directly involved in the conduct of the study.
17. Pregnant female patients; breastfeeding female patients, female patients of childbearing potential and fertile male patients (Part 1A and Part 1C only) who are unwilling or unable to use 2 highly effective methods of contraception as outlined in this protocol for the duration of the study and for at least 28 days after the last dose of investigational product.
18. Active inflammatory gastrointestinal (GI) disease, known diverticular disease or previous gastric resection or lap-band surgery. Impairment of gastro-intestinal

function or GI disease that may significantly alter the absorption of PF-06873600, such as history of GI surgery with may result in intestinal blind loops and patients with clinically significant gastroparesis, short bowel syndrome, unresolved nausea, vomiting, active inflammatory bowel disease or diarrhea of CTCAE Grade >1. Gastroesophageal reflux disease under treatment with proton-pump inhibitors is allowed.

19. Current use of drugs as shown in [Appendix 5](#), which have a risk for QTc prolongation.
20. Current use or anticipated need for food or drugs that are known strong CYP3A4/5 inhibitors, including their administration within 5 half-lives of the CYP3A4/5 inhibitor, prior to first dose of investigational product. Current or anticipated use of moderate CYP3A4/5 inhibitors (including their administration within 5 half-lives of the CYP3A4/5 inhibitor, prior to first dose of investigational product) should be avoided if possible, and any use will need to be reviewed and approved by the Sponsor (See [Section 5.7](#)).
21. Current use or anticipated need for drugs that are known strong CYP3A4/5 inducers, including their administration within 5 half-lives of the CYP3A4/5 inducer, prior to the first dose of investigational product (See [Section 5.7](#)).

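### Section 5.7 restricts strong CYP3A4/5 inhibitors and inducers only up to the first dose, so no general written rule applies once PF-06873600 dosing has started

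*Protocol*

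**What the plan says.** Section 5.7 of the protocol starts from permission: concomitant treatment judged necessary for the patient "may be given at discretion of the treating physician". It then sets class rules.

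- Strong CYP3A4/5 inhibitors: "the use of known strong CYP3A4/5 inhibitors is not permitted within 5 half-lives of the respective CYP3A4/5 inhibitor(s), prior to the first dose".
- Strong inducers: "the use strong CYP3A4/5 inducers is not permitted within" five half-lives of the inducer before the first dose.
- Moderate inhibitors: to be avoided if possible, and "any use needs to be reviewed and approved by the sponsor". No time limit is attached.
- Moderate inducers: caution.

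Section 4.2 adds entry criteria. Criterion 20 excludes "Current use or anticipated need for food or drugs that are known strong CYP3A4/5 inhibitors", and criterion 21 excludes "Current use or anticipated need for drugs that are known strong CYP3A4/5 inducers".

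Some on-treatment limits exist elsewhere. Section 5.7.1 bars listed herbal supplements. Sections 5.7.5 and 5.7.6 allow anti-diarrheals, anti-emetics, anti-inflammatories and narcotic analgesics only if no interaction is expected and the drug is not named in the concomitant-treatment section. Section 5.4.3.2 and Appendix 6 advise considering interactions for drugs given for SARS-CoV2 infection.

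Section 5.7 lists cimetidine among the moderate inhibitors. Section 5.7.9 lists it as a permitted H2 antagonist without mentioning approval.

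**The concern.** Section 1.3.2 describes clearance of PF-06873600 as "oxidation mediated primarily by cytochrome P450 (CYP) enzymes, predominantly CYP3A4". Section 5.7 explains its rules by the risk that inhibition raises exposure and toxicity and that induction lowers efficacy. Both effects need the drug to be on board, yet the rule for the strongest modulators, read literally, stops at the first dose.

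A need that arises later is foreseeable. Criterion 10 excludes active infection at entry, while the DLT definition in Section 3.1.6 anticipates febrile neutropenia and neutropenia with infection on treatment. Several of the named strong inhibitors are antifungals or antibacterials. A site following the text would ask the sponsor before giving fluconazole (listed as moderate) but would find no general rule for ketoconazole or clarithromycin (listed as strong). What is at stake is patient safety through uncontrolled exposure, or lost efficacy through induction. No statistical operating characteristic of the trial is at issue.

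**Working it through.** No stated figure is to be reproduced, so the check sets the rules side by side.

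| Class in Section 5.7 | Named drugs | At entry | After the first dose |
|---|---|---|---|
| Strong inhibitors | 18, plus grapefruit and related citrus | Washout of 5 half-lives; current use or anticipated need excluded (criterion 20) | No general rule |
| Strong inducers | 8 | Washout of 5 half-lives; current use or anticipated need excluded (criterion 21) | No general rule; St. John's Wort barred by Section 5.7.1 |
| Moderate inhibitors | 12 | Avoid; sponsor approval | Sponsor approval for any use |

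**Do the narrower rules close the gap?** None of the listed strong inhibitors or inducers is an anti-diarrheal, anti-emetic, anti-inflammatory or narcotic analgesic, so Sections 5.7.5 and 5.7.6 do not reach them. Section 5.7.1 reaches one strong inducer. That leaves 8 − 1 = 7 strong inducers and 18 strong inhibitors, or 25 of 26 named drugs, without a general on-treatment restriction. The SARS-CoV2 text is advice for one indication.

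**Do the entry criteria reduce the need?** Partly. Seven of the 18 strong inhibitors are HIV protease inhibitors (indinavir, saquinavir, ritonavir, nelfinavir, amprenavir, fosamprenavir, lopinavir), and criterion 10 excludes known HIV with a limited exception for negative viral load. Three of the 7 remaining inducers are anticonvulsants (phenobarbital, phenytoin, carbamazepine), and criterion 1 requires patients with a history of CNS metastases or cord compression to be stable off anticonvulsants. Setting both groups aside leaves 25 − 7 − 3 = 15 drugs. These criteria make use less likely; they do not restrict it.

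**Is the literal reading strained?** Sections 5.7.3 and 5.7.5 bar prophylaxis before Cycle 1 Day 1 and then expressly allow therapeutic use afterwards. Section 5.7.1, where an on-treatment bar is meant, refers to the time on study treatment and to concurrent use. A site therefore has grounds for reading a limit tied to the first dose as ending there.

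These counts describe scope only. The documents give no frequency of use and no size for the exposure change, so no risk can be calculated.

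**The case against.** The strongest reply is that the intent is plain. Excluding patients with an anticipated need makes sense only if use during dosing is unwanted. The rationale in Section 5.7 concerns dosing, and Sections 5.7.5 and 5.7.6 treat drugs named in the concomitant-treatment section as disallowed on treatment. This stands as evidence of intent. A reader might infer from the contrast with moderate inhibitors that the sponsor chose to control strong ones less; the documents do not support that. They support only that the intended rule is not written for the period in which it matters.

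Three further inferences are tempting and should not be drawn.

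- **QT drugs need an on-treatment ban.** Criterion 19 does cover only "Current use of drugs as shown in" Appendix 5. However, the main schedule has triplicate ECGs on Day 1 of each cycle and on Cycle 1 Days 8 and 15 and Cycle 2 Day 8. Section 7.1.5 has rules for correcting co-medication, holding, reducing and removing, and Section 1.3.3 reports no nonclinical QT effect. The scheduled ECGs do fall away under the Amendment 9 schedule, but that alone does not show that a ban, or an edit to criterion 19, is needed.
- **Dose finding was distorted.** Interaction-driven DLTs could in principle count, because the listed major treatment deviations in Section 9.1 do not mention these drugs. Whether such a patient stays evaluable is itself an inference, since that list is introduced as inclusive. Counting such a DLT would err toward a lower dose. Appendix 7.1 reports no DLTs at the 25 mg IR monotherapy RDE.
- **Section 5.7.4 opens a separate gap for oral antibiotics.** Moderate inhibitors already need approval for any use, and strong ones would be covered by the main correction.

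It is also fair that the study was terminated on 07 September 2022 and that few beneficiaries may remain. This limits the value of the change but does not make the sentence right.

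**Conclusion.** The point holds as a wording gap with a safety purpose. Section 5.7 states a rule for strong CYP3A4/5 modulators whose time window ends when the reason for it begins. Outside St. John's Wort and the classes in Sections 5.7.5 and 5.7.6, nothing written restricts a strong modulator first needed on treatment. The cimetidine mismatch is only a missing cross-reference, since approval for any use of a moderate inhibitor already covers it.

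The conclusion rests on reading the text as a site would follow it, and on no separate instruction to sites outside the documents. The size of the risk is unknown. The benefit is confined to patients still receiving PF-06873600 under Amendment 9, whose number is not given and for whom treatment may run until 31 October 2024 at the latest. It is a cheap improvement.

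**What to change.** In Section 5.7, state that strong CYP3A4/5 inhibitors and inducers are not permitted from 5 half-lives before the first dose through the last dose of PF-06873600. Any medically unavoidable use should be discussed with the sponsor, and PF-06873600 interrupted or discontinued as appropriate. An automatic interruption rule would be too rigid: for a modulator needed long term, interruption has no end and amounts to discontinuation.

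Repeat the rule in Appendix 8. That appendix carries forward Section 5.4 for dosing and Section 8 for SAE reporting but does not mention Section 5.7. In Section 5.7.9, make cimetidine subject to the approval rule.

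The cost is one wording amendment, with IRB/EC approval under Section 12.1, plus occasional interruption or discontinuation when a strong modulator cannot be avoided. Section 5.4.3.1 already refers non-toxicity interruptions lasting 4 weeks to the sponsor for the decision to resume. No new data are required. The Amendment 9 schedule has no concomitant-medication entry, so it would not capture adherence to the rule.

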5.7.1. Other Anti-tumor or Experimental Drugs

No additional anti-tumor treatment will be permitted while patients are receiving study treatment. Additionally, the concurrent use of select herbal supplements (including those listed in [Section 5.7](#)) is not permitted.

Palliative radiotherapy on study is permitted for the treatment of painful bony lesions provided that the lesions were known at the time of study entry and the investigator clearly indicates that the need for palliative radiotherapy is not indicative of disease progression. In view of the current lack of data about the interaction of PF-06873600 with radiotherapy, PF-06873600 treatment should be interrupted during palliative radiotherapy, stopping 3 days or 5 half-lives (whichever is longer) before and resuming treatment after recovery to baseline.

5.7.2. Supportive Care

Palliative and supportive care for disease related symptoms may be administered at the investigator's discretion and according to available American Society of Clinical Oncology (ASCO) guidelines.

Female patients currently being treated with a gonadotropin-releasing hormone agonist (GnRH agonist) prior to study enrollment may continue treatment while on study treatment as long as the GnRH agonist treatment has been well tolerated for at least 3 months prior to study entry.

5.7.3. Hematopoietic Growth Factors

Primary prophylactic use of granulocyte-colony stimulating factors is not permitted prior to Cycle 1, Day 1 (C1D1), but they may be used to treat treatment emergent neutropenia as indicated by the current ASCO guidelines. For Japan only: since the indication and dosage of G-CSF compounds approved in Japan may differ from ASCO guidelines, refer to Japanese package insert and local clinical guideline.

Erythropoietin may be used at the investigator's discretion for the supportive treatment of anemia (Note: erythropoietin is not approved for anemia caused by chemotherapy in all local regions, nor is it currently approved in Japan).

5.7.4. Diarrhea Management

Diarrhea is a possible adverse event based on the preclinical toxicology data. As there is no prior clinical experience with PF-06873600, the exact nature of treatment related diarrhea in humans is unknown. In general, management of cancer treatment-induced diarrhea have been described (Benson et al, 2004).²⁸ Initial management for mild to moderate diarrhea may include dietary modifications (eliminating lactose and other high-osmolar dietary supplements), loperamide or diphenoxylate/atropine, along with oral antibiotics if persistent with concern for infection. Management of higher severity or more complicated diarrhea may also include consideration of intravenous fluids for hydration, electrolyte replacement, octreotide, stool workup along with hospitalization for observation and treatment if indicated in the investigator's medical judgment.

5.7.5. Anti-Diarrheal, Anti-Emetic Therapy

Primary prophylaxis of diarrhea, nausea and vomiting is not permitted prior to C1D1. Anti-diarrheal and anti-emetic therapies may be used to treat treatment emergent diarrhea, nausea and vomiting as early as during Cycle 1. The choice of the drug as well as the duration of treatment is up to the investigator, assuming there is no known or expected drug-drug interaction and assuming the drug is not included in the [Concomitant Treatment\(s\)](#) section.

5.7.6. Anti-Inflammatory Therapy

Anti-inflammatory or narcotic analgesic may be offered as needed assuming there is no known or expected drug-drug interaction and assuming the drug is not included in the [Concomitant Treatment\(s\)](#) section.

5.7.7. Corticosteroids

Chronic systemic corticosteroid use for palliative or supportive purposes is not permitted. Acute emergency administration, topical applications, inhaled sprays, eye drops, or local injections of corticosteroids are allowed.

